4 INVESTIGATIONAL PLAN

4.1 Overall Study Design and Plan

This is a controlled, randomized, two-arm, open-label, assessor-blinded, multicenter study to determine the effect on clinical parameters of neurodevelopmental status of monthly IT administration of idursulfase-IT for 12 months in pediatric patients with Hunter syndrome and early cognitive impairment who have previously received and tolerated a minimum of 4 months of therapy with Elaprase.

All patients will continue to receive Elaprase therapy as standard of care throughout the study.

The pivotal study design is “no IT treatment-controlled”. Approximately 48 patients will be randomized in a 2:1 ratio to IT treatment or no IT treatment arms.

Those patients randomized to the IT treatment arm will undergo surgical implantation of the SOPH-A-PORT Mini S IDDD followed by a post-operative recovery period of at least 14 days prior to the first IT administration of idursulfase-IT. Treated patients will then receive 12 monthly IT injections of 10 mg idursulfase-IT corresponding to a treatment and assessment interval of 13 (28-day) months from randomization to the end-of-study (EOS) evaluations. Likewise, patients randomized to the no IT treatment arm will be assessed over 13 (28-day) months after randomization.

The separate substudy is open label and single arm. Patients who are enrolled in the substudy will follow a similar schedule of study visits as idursulfase-IT-treated patients in the pivotal study.

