4.1.1 Intrathecal Drug Delivery

It is planned that the study drug, idursulfase-IT (HGT-2310) will be administered to patients via the SOPH-A-PORT[®] Mini S, Implantable Access Port, Spinal, Mini Unattached, with Guidewire (SOPH-A-PORT Mini S), manufactured by Sophysa SA (Orsay, France) or, alternatively, via lumbar puncture in the event of device malfunction. This IDDD will be used to obtain CSF samples and to deliver IT injections of idursulfase-IT.

If the IDDD appears to be non-functional, or if its use is precluded on a scheduled day of dosing, site personnel will refer to the IDDD Manual, which provides details on the investigation and management of any IDDD-related issues. This includes possible partial revision or complete replacement of the IDDD as indicated. If the intrathecal space is not accessible via the IDDD, study drug may be administered to a patient by lumbar puncture up to 12 times. Should the IDDD become clogged, undergo mechanical complications, or otherwise not be accessible, the CSF sample may also be obtained from a patient by lumbar puncture up to 12 times during the treatment phase of the study.

General anesthesia/sedation may be required for injections of study drug and some evaluations, and may be used at the discretion of the Investigator.

A Data Monitoring Committee (DMC) will oversee both idursulfase-IT and device safety. The DMC will be notified of IDDD failures and related complications on a periodic basis according to the DMC charter (See Section 11.8).

Patients will have the IDDD removed when they discontinue from the study, unless the patient is continuing to receive treatment through another mechanism (eg, extension study, expanded access program).

See Section 13 for the Schedule of Events (SOE) for the pivotal study ([Appendix 1](#) and [Appendix 2](#)) and separate substudy ([Appendix 3](#)).

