	
Behavior Index and its subscales (Internalizing, Externalizing)
 
Exploratory efficacy endpoint
 
 • Slope estimate from the linear regression of GCA scores over time for each subject 
Additional efficacy endpoint for substudy only
 
 • Observed value in raw score, age equivalents versus chronological age, as well as DQ, composite score and percentile for the three scales of the BSID-III (Motor [Fine, Gross], Language [Receptive, Expressive], Cognitive) for substudy only 
Pharmacokinetic and Pharmacodynamic endpoints
 
 • Serum concentration of idursulfase and serum PK parameters after IT administration • CSF concentration of idursulfase prior to each monthly IT administration • Change from baseline in the concentration of GAG in CSF 
Safety Assessments
 
Safety will be assessed during the study by collection of adverse events (by type, severity, and relationship to treatment [idursulfase-IT, the IDDD, device surgical procedure, or IT administration process] and IV Elaprase infusion), changes in clinical laboratory testing (serum chemistry, hematology, urinalysis), physical and neurological examination, vital signs, 12-lead ECG, CSF laboratory parameters (chemistries, cell counts), anti-idursulfase antibodies in CSF and serum, and determination of antibodies having enzyme neutralizing activity.
 
SOPH-A-PORT[®] Mini S Device Assessments
 
The SOPH-A-PORT Mini S device will be evaluated using assessments of device implantation, device function, device longevity and adverse events associated with the implant surgery or device. Those data will be collected on the patient's electronic case report form (eCRF) from the time of initial implantation and continue throughout the study as long as the SOPH-A-PORT[®] Mini S remains implanted.
 
Health Status Assessment
 
Health status dimensions as obtained by the EQ-5D questionnaire: mobility, self-care, usual activities, pain/discomfort, and anxiety/depression.

Number of Subjects	
Pivotal study
 
 • 48 male patients (32 IT treated and 16 No IT treatment) are planned.

	
Substudy
 
 • There is no pre-specified number of patients planned. The enrollment will conclude when enrollment of patients in the pivotal study closes.

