6.6 Treatment Compliance and Extent of Exposure

The number of IT injections received overall and by lumbar puncture, average dose, the duration of idursulfase-IT treatment and IT administration duration will be summarized descriptively in the idursulfase-IT arm.

The duration of idursulfase-IT treatment, summarized in months, is defined as the time from first to last IT administration during the study.

The duration for each idursulfase-IT administration (in minutes) is calculated by subtracting the administration start time from the administration end time. The actual average duration of idursulfase-IT administration (in minutes) will be calculated as an average value of the idursulfase-IT administrations across all available administrations for the same patient.

Treatment compliance will be summarized in terms of the percent of scheduled doses received in the idursulfase-IT arm. The percent of scheduled doses received for each patient is defined as: $[(\text{Number of Complete IT injections Received}) \div (\text{Expected Number of IT injections at EOS})] * 100$.

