The AE categories 1-7 will be presented by each treatment group for patients in the Safety Population, while the AE categories 8-12 will be presented by each treatment group for patients in the Safety Population who received idursulfase-IT. IT administration process-related AEs will be summarized by IT administration method (LP or IDDD) as well. The AE categories 10-11 will be presented for patients in the Safety Population with the device implanted. The number and proportion of patients, and the number of corresponding AEs will be summarized in overall summary tables. In addition, the number and percentage of patients having any treatment-emergent AE within the AE categories 2, 5, 7-12 and the number of corresponding AEs will be displayed by MedDRA system organ class (SOC), preferred term (PT) and treatment group. The most common treatment-emergent AEs which happened in >10% patients in either treatment group will also be summarized by SOC and PT. The most common non-serious treatment-emergent AEs which happened in >5% patients in either treatment group will also be summarized by SOC and PT.

The number and percentage of patients having any treatment-emergent AE, and the number of corresponding AEs will be summarized by MedDRA SOC, PT and severity.

The number and percentage of patients having any treatment-emergent AE, and the number of corresponding AEs will be summarized by relationship to IV Elaprase, idursulfase-IT, and at least one IT treatment regimen, and summarized by MedDRA SOC and PT.

Furthermore, listings of all the AEs of categories 3-6 will be provided if applicable.

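### The LP-versus-IDDD split of administration-process adverse events has no exposure denominator, so it partly reflects how often each route was used

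*SAP*

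**What the plan says.** SAP 6.8.1 lists events related to the IT administration process as category 12 and adds a split by route: "IT administration process-related AEs will be summarized by IT administration method (LP or IDDD) as well". For the categories in general, "The number and proportion of patients, and the number of corresponding AEs will be summarized in overall summary tables". The population is also stated: "AE categories 8-12 will be presented by each treatment group for patients in the Safety Population who received idursulfase-IT". Categories 10 and 11 are then restricted to boys with the device implanted, but no matching restriction to boys exposed to a given route is set for the split of category 12. No rate per injection is named.

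Injection counts appear elsewhere. SAP 6.6 will summarise "The number of IT injections received overall and by lumbar puncture", without linking this to the adverse event tables.

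On exposure, the SAP gives "48 male patients (32 IT treated and 16 No IT treatment) are planned" and protocol 4.1 says "Treated patients will then receive 12 monthly IT injections of 10 mg idursulfase-IT". The planned route is the port "or, alternatively, via lumbar puncture in the event of device malfunction" (protocol 4.1.1). The same section allows that "study drug may be administered to a patient by lumbar puncture up to 12 times". Protocol 8.3.1 also notes US patients who were dosed by LP before the device could be implanted; it does not say how many.

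**The concern.** A boy can receive some doses through the port and others by LP. Whether he has at least one process-related event on a route depends on the risk per administration and on how many administrations he had by that route. A raw event count has the same dependence. Two routes with identical risk per injection will therefore show different figures whenever they are used unequally, and the plan expects unequal use.

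This is the only split of adverse events by route in the SAP. Protocol 1.2 and 1.3.1 justify the port by the wish to avoid repeated LPs and repeated general anesthesia, so readers will look at this table when they weigh the two ways of giving the drug. Without an exposure denominator it can mislead them in either direction.

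**Working it through.** The documents give no figure on this point, so there is none to reproduce. The check asks what the planned measures would show if both routes carried the same risk.

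**Inputs from the documents.** 32 treated boys (SAP 4.1) and 12 injections each (protocol 4.1), so 32 × 12 = 384 injections if all are given.

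**Assumptions, not in the documents.** Risk p per injection, equal on both routes and independent between injections, from 1% to 10%; k LP doses and 12 − k IDDD doses per boy.

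**Formulas.** Patients with at least one event: LP 1 − (1 − p)^k; IDDD 1 − (1 − p)^(12 − k). Ratio of event counts, IDDD to LP: (12 − k)/k.

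Each cell gives LP %, IDDD % and the IDDD/LP ratio:

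| LP doses of 12 | p = 1% | p = 5% | p = 10% | Event-count ratio |
|---|---|---|---|---|
| 1 | 1.0, 10.5 (10.5) | 5.0, 43.1 (8.6) | 10.0, 68.6 (6.9) | 11 |
| 2 | 2.0, 9.6 (4.8) | 9.8, 40.1 (4.1) | 19.0, 65.1 (3.4) | 5 |
| 3 | 3.0, 8.6 (2.9) | 14.3, 37.0 (2.6) | 27.1, 61.3 (2.3) | 3 |
| 4 | 3.9, 7.7 (2.0) | 18.5, 33.7 (1.8) | 34.4, 57.0 (1.7) | 2 |
| 6 | 5.9, 5.9 (1.0) | 26.5, 26.5 (1.0) | 46.9, 46.9 (1.0) | 1 |
| 9 | 8.6, 3.0 (0.34) | 37.0, 14.3 (0.39) | 61.3, 27.1 (0.44) | 0.33 |

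**Effect of the denominator when only some boys have an LP (p = 5%).** Suppose 25% of boys have LP doses and the rest have all 12 by IDDD.

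| LP doses in those boys | Ratio, all treated boys as denominator | Ratio, boys exposed to the route |
|---|---|---|
| 2 | 18.3 | 4.6 |
| 6 | 6.2 | 1.6 |
| 12 | 3.0 | 1.0 |

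For the first row: IDDD 0.25 × 40.1% + 0.75 × 46.0% = 44.5%; LP 0.25 × 9.75% = 2.44% of all boys, or 9.75% of exposed boys. Hence 44.5/2.44 = 18.3 (unrounded inputs) and 44.5/9.75 = 4.6. Restricting to exposed boys reduces the distortion but does not remove it.

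**With an injection denominator.** Take p = 5%, 2 LP and 10 IDDD doses per boy, 32 boys. LP: 64 injections, 64 × 0.05 = 3.2 expected events, 5.0 per 100. IDDD: 320 injections, 16 expected events, 5.0 per 100. The ratio is 1.0, where the planned measures show 9.8% against 40.1% of patients and 3.2 against 16 events.

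**Non-dosing LPs.** Protocol 7.14.1.5 counts LP complications as process events. LPs are also done without dosing: for CSF sampling when the port cannot be used (protocol 7.5.3) and for intracranial pressure at end of study (protocol 7.11.7 and 8.4.1). The latter could add 32 × 1 = 32 LPs in the treated arm, inside the SAP 6.8.1 treatment-emergent window. That is as many as the dosing LPs if each boy has one. A rule that charges each event to the last dosing route would count an end-of-study LP complication against the port whenever the Week 48 dose went through it.

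**The case against.** The strongest reply has four parts.

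- **The LP share is unknown.** LP may cover every dose, and some US boys started on LP. This stands. A reader might infer that LP is bound to look several times safer. The documents do not support that: it needs about 1 to 3 LP doses of 12 per boy, which is an assumption.
- **No comparison with LP is promised.** This also stands. A reader might take device-versus-LP safety to be a stated device objective, but protocol 2.4 concerns the device's own safety and performance and names no comparison. Category 12 alone could not settle the question; device harm is also covered by categories 10 and 11 and by the failure analyses in SAP 6.8.6.7. SAP 6.8 makes all safety analyses descriptive.
- **A reader can derive the rate.** Event counts are planned, and SAP 6.6 gives total and LP injections, so IDDD injections follow by subtraction. This is partly right, but it does not cure a by-route table printed without its exposure. It also gives no correct patient denominator and no separation of non-dosing LPs. SAP 6.8.1 plans listings only for categories 3 to 6, and SAP 8.9 limits further by-patient listings.
- **The table layout is not visible.** The shells are separate documents (SAP 9.1) and may show injection counts. That is possible, but the SAP text does not require it.

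**Conclusion.** The point holds as a defect of presentation in a descriptive safety table, worth correcting before the tables are produced. The route split lacks an exposure denominator, and the population stated for category 12 would put boys who never had an LP into the LP percentage.

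Under equal and independent risk per injection of 1% to 10%, all 12 doses given and 1 to 3 of them by LP in each boy, the apparent IDDD/LP ratio of patient percentages runs from 2.3 to 10.5, and of event counts from 3 to 11. At 6 LP doses there is no distortion; at 9 it runs the other way (0.34 to 0.44). Because the LP share is not given, the safe statement is that the table cannot be read as a comparison of risk by route.

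No hypothesis test, error rate or efficacy conclusion is affected. The SAP already uses exposure for a neighbouring quantity: its overall device failure rate divides by time at risk (SAP 6.8.6.7). Protocol 10.7.7.3 likewise builds the device success rate on injections.

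**What to change.** Amend the route split in SAP 6.8.1 as follows.

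1. Report process-related events per 100 administrations by that route, with the number of injections and the number of boys exposed to each route in the same table.
2. Base any patient percentage on boys exposed to that route.
3. Assign each event to the procedure it followed. Show complications of non-dosing LPs (CSF sampling, end-of-study pressure measurement) on a separate line, not under the last dosing route.
4. Give a simple exact interval or none. LP events may be very few (3.2 expected in the example above), so intervals that model clustering by patient are optional.

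The cost is a few sentences of SAP text and one table shell. LP injections are already to be counted under SAP 6.6, and protocol 7.6 has the date and times of each injection recorded. The added work is mainly linking events to procedures.

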6.8.2 Clinical and CSF Laboratory Evaluations

Chemistry and hematology serum laboratory and CSF (standard chemistries, glucose, protein, and cell counts) values will be summarized in terms of the absolute value and change from baseline at each scheduled study visit by treatment group. The total protein, glucose and total nucleated cells will be plotted for individual patients over time by scheduled study visit.

All the laboratory (chemistry, hematology, urinalysis and CSF) values will be categorized as a patient having had (1) a Clinically Significant (CS) value at any time during the study post baseline, and (2) no CS values at any time during the study post baseline. The number and percentage of patients in each category will be presented by treatment dose and overall. Patients with a Normal or non-CS value for a particular laboratory parameter at baseline who experience a change to CS for that laboratory parameter post-baseline will be identified and listed separately along with the corresponding laboratory values over time. The baseline is defined as the Screening measurement. If it is not available, the Pre-Surgery Day 1 of Week 1 measurement will be used as baseline.

If a particular laboratory measurement has been either repeated or retested, then the repeated or retested measurement for that laboratory parameter, with respect to date/time, will be used in the statistical analysis unless this value is invalid/missing. The handling of repeated or retested laboratory measurements should only consider the specific laboratory measurement that was repeated or retested.

6.8.3 12-Lead ECG Evaluations

The 12-lead ECG parameters (heart rate [bpm], PR interval [msec], QRS interval [msec], QT interval [msec] and the corrected QT interval (QTc) [msec]) will be summarized in terms of absolute value and change from baseline by visit and treatment group. The QTc interval will be calculated using Bazett's formula as QT divided by the square root of RR interval. The number and percentage of patients with ECG abnormalities post baseline will be presented by treatment group.

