8.3 Treatment Period (Months 1 to 12)

During this period, several phases of activity will occur. These are designated in the SOE as: Pre-surgery, Surgery, Follow-up, and Post-op Recovery at Week 2 (+7 days) and IT Dosing at Weeks 4, 8, 12, 16, 20, 24, 28, 32, 36, 40, 44, 48 [± 7 days] (Pre-treatment, IT Injection, Follow-up).

8.3.1 Patients in the IT Treatment Group of the Pivotal Study and All Patients in the Substudy: Pre-surgery, Surgery, Follow-up, and Post-op Recovery (Week 2 [+7 days])

IDDD placement will require surgical implantation under general anesthesia and post-surgical assessment.

Note: Patients in the USA who were randomized in the pivotal study prior to FDA authorization of investigational use of the SOPH-A-PORT Mini S IDDD and treated with idursulfase-IT via lumbar puncture will have the assessments originally planned at Week 2 [+7 days] performed at the time of the delayed device implantation surgery.

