8.3.1.1 Pre-surgery

- Physical and neurological examination*
- Height and weight*
- 12-lead ECG*
- Vital signs*
- Clinical laboratory tests (hematology, serum chemistry, urinalysis)*
- Coagulation tests ([PT, PTT] to be performed by the local laboratory)
- Concomitant medications, therapies/interventions, and medical/surgical procedures
- Adverse events

*The assessments indicated do not need to be repeated if completed as part of Screening assessments within 7 days prior to surgery.

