8.3.1.2 Surgery

- Vital signs
- General anesthesia
- CSF sample collection
- IDDD implantation
- X-ray (to verify IDDD is at the mid-thoracic level in the spinal canal and correctly installed)
- Concomitant medications, therapies/interventions, and medical/surgical procedures
- Adverse events

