- ^r The follow-up visit is to occur on the day after IT administration during the first 6 months of IT treatment (ie, at Weeks 4, 8, 12, 16, 20, 24). For the latter 6 months of treatment with idursulfase-IT (ie, from Week 28 onward) and in the absence of any safety concerns, patients may complete the safety follow-up visit on the same day as IT administration prior to discharge.
- ^s The assessments indicated do not need to be repeated if completed as part of Screening assessments within 7 days prior to surgery.
- ^t The results of patients' genotype analyses must be known prior to randomization (See Section 7.3.1).
- ^u Patients in the USA who were randomized in the pivotal study prior to FDA authorization of investigational use of the SOPH-A-PORT Mini S IDDD and treated with idursulfase-IT via lumbar puncture will have the assessments originally planned at Week 2 [+7 days] performed at the time of the delayed device implantation surgery.

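### The fallback laboratory baseline in SAP 6.8.2 names a visit that does not exist and is not required to precede the first IT dose, so for early US lumbar-puncture patients it can select an on-treatment value

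*SAP*

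**What the plan says.** SAP 6.8.2 covers serum chemistry, hematology, urinalysis and CSF. It states "The baseline is defined as the Screening measurement" and then gives the fallback: "If it is not available, the Pre-Surgery Day 1 of Week 1 measurement will be used as baseline". It attaches no condition about the first dose.

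Protocol 8.3.1 makes an exception for some US patients in the pivotal study. Those randomized "prior to FDA authorization of investigational use of the SOPH-A-PORT Mini S IDDD and treated with idursulfase-IT via lumbar puncture" are to be handled differently: they "will have the assessments originally planned at Week 2 [+7 days] performed at the time of the delayed device implantation surgery". Appendix 1 footnote u repeats the exception for "Patients in the USA who were randomized in the pivotal study prior to FDA authorization of investigational use of the SOPH-A-PORT Mini S IDDD".

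The assessments that move include laboratory work. In Protocol 8.3.1.1 the pre-surgery list has an entry beginning "Clinical laboratory tests (hematology, serum chemistry, urinalysis". It has no CSF entry. "CSF sample collection" appears in the next list, Protocol 8.3.1.2 (Surgery).

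**The concern.** A fallback baseline is useful only if it predates treatment. The pre-surgery sample does so on the usual schedule, with surgery at Week 2 and the first dose at Week 4. In the early US lumbar-puncture patients the order is reversed: dosing starts first, and the sample still called pre-surgery is drawn later.

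If the Screening value of an analyte is missing in such a patient, three outputs of SAP 6.8.2 can be affected:

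- **Change from baseline** is measured from an on-treatment value.
- **The count of patients with a clinically significant value after baseline** omits a significant result at that draw, because the draw is now the baseline.
- **The listing of shifts from normal or not clinically significant to clinically significant** cannot include the patient for that analyte if the substituted baseline is itself clinically significant.

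If implantation was delayed beyond a scheduled on-treatment draw, such as Week 16, that result would also predate the baseline. The SAP does not say how to treat it.

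**Working it through.** There is no figure in the plan to reproduce. The check sets the two schedules beside the SAP rule.

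| Step | Usual IT-arm schedule | US patients dosed by lumbar puncture before device authorization | Source |
|---|---|---|---|
| Screening laboratory tests | Day -28 to Day -1 | Same | Protocol 8.1.1 |
| Pre-surgery laboratory tests | Week 2 (+7 days) | At the delayed implantation | Protocol 8.3.1, 8.3.1.1; Appendix 1 footnote u |
| Week 4 laboratory tests | Before the Week 4 injection | Same | Protocol 8.3.2.1 |
| Is the pre-surgery sample before the first IT dose? | Yes | No | Follows from the rows above |

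1. **Does the label exclude the late sample?** No scheduled visit is called Day 1 of Week 1. Read literally, the fallback selects nothing. A programmer who has to map it will most naturally choose the visit named Pre-surgery. SAP 8.8 uses nominal visits for per-visit analyses, and no date check is stated, so nothing stops the late sample from being chosen.

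2. **Would the late sample exist?** Protocol 8.3.1.1 waives the pre-surgery laboratory tests only when Screening tests were done within the 7 days before surgery. After a delayed implantation that waiver is unlikely to apply, so the sample would normally be drawn.

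3. **Does the SAP know that dosing can precede implantation?** Yes. SAP 6.8.1, 6.8.7 and 6.8.8 start the IT-arm window for treatment-emergent adverse events, concomitant medications and concomitant therapies at the earlier of first implant surgery and first dose. The fallback in 6.8.2 lacks that anchor.

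4. **Is a better sample available?** For these patients the Week 4 tests are listed as pre-treatment, ahead of the scheduled injection. The present rule passes over them.

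5. **What of CSF?** The pre-surgery list has no CSF sample, so the CSF fallback is undefined as worded. If the CSF sample taken at surgery were used instead, it too would be post-dose in these patients.

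6. **What of controls?** Week 2 is a telephone contact for them, and it does not apply at all to US controls randomized before authorization (Protocol 8.3.3.1). The fallback can operate only in the IT arm.

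7. **Size.** The effect needs two things together: a missing Screening value for the analyte, and membership of the early US group. The documents give neither the size of that group nor any rate of missing Screening values.

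**The case against.** The case for leaving this alone is strong on frequency and on consequence.

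- **The trigger is nearly closed by design.** Screening laboratory tests are scheduled for everyone, and Appendix 1 footnote b places randomization after Screening is complete. Protocol section 7 allows re-testing during Screening, and SAP 6.8.2 uses a repeated or retested value unless it is invalid or missing. The fallback therefore needs a lost or unreportable analyte in a small, closed group. Nothing in the documents shows that this happened. This stands.
- **The label may not select the late sample.** True on a literal reading, but the fallback would then do nothing for anyone. That is a defect of its own.

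A reader might also draw three stronger conclusions. The documents support none of them.

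- **That the rule hides toxicity in the treated arm.** Protocol 7.14.1.1 counts clinically significant abnormal laboratory values as adverse events, and SAP 6.8.1 opens the IT-arm window at the first dose when that comes before implantation. Such a result is still reported. Absolute values are also summarized by visit.
- **That the distortion runs in one direction.** A persistent shift would be masked. A shift that was present at the late draw and then resolved would produce an apparent change the other way. A substituted baseline that is not clinically significant does not remove later significant results.
- **That a probability can be attached.** With n early US IT-arm patients and a proportion m of Screening values missing independently, the chance of at least one affected patient for an analyte is 1 - (1 - m)^n. Assuming n = 3 and m = 2% gives 0.06; assuming n = 10 and m = 10% gives 0.65. Both inputs are assumptions, so the spread only reflects what was put in.

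**Conclusion.** The fallback rule is faulty as written. It names a visit that the protocol does not have, and it lacks a pre-dose condition that the SAP applies elsewhere. For hematology, chemistry and urinalysis in the early US lumbar-puncture patients it can select an on-treatment value; for CSF it is undefined.

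The point is minor. It should be rare, and its size cannot be derived. SAP 6.8 makes all safety analyses descriptive, so the primary endpoint and the type I error rate are untouched. What could be wrong is the change-from-baseline summary, the post-baseline count and the shift listing, for particular analytes in particular patients.

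The conclusion rests on two readings: that the mislabelled visit would be mapped to Pre-surgery, and that these patients received at least one lumbar-puncture dose before implantation, as Protocol 8.3.1 describes.

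**What to change.** Replace the fallback sentence in SAP 6.8.2 with a date rule:

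> If the Screening value is missing, baseline is the last non-missing value before the earlier of the first IDDD implant surgery and the first IT dose (IT arm), or on or before randomization (control arm); otherwise baseline is missing.

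Delete the Day 1 of Week 1 label, and state that the same date rule applies to CSF.

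On the usual schedule the rule still picks the pre-surgery sample for blood and urine. For patients dosed first by lumbar puncture it can pick the Week 4 pre-treatment sample.

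The cost is one sentence and one programming condition, with times compared when a sample and the surgery share a date. There are three limits:

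- A few patients may have no baseline for an analyte.
- CSF taken during the first implantation is not strictly before surgery. A patient on the usual schedule who lacks a Screening CSF value would normally have no CSF baseline.
- The difference between arms remains. Screening is the only scheduled laboratory draw before randomization, so a control whose Screening value is missing will normally still have no fallback.
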